3.7 SRS Toxicity Profile

Multiple studies reported low risk of toxicity after spinal SRS. The majority of events involved Grade 1 or 2 skin and esophageal toxicity²¹. To date, hypofractionated treatment of the spine has not been reported to result in Grade 3 or 4 neurologic toxicity. Single cases of Grade 3 vomiting, diarrhea, costochondritis and dysphagia were reported after hypofractionated treatment^{29,30}. To date, radiation literature describes nine cases of radiation myelopathy that have been attributed to single-fraction spinal radiation, confirming that this is an exceedingly rare consequence of spinal radiation³¹. Furthermore, in this institution no cases of radiation-induced myelopathy have been observed using cord point-maximum dose of 14Gy in patients without prior radiation history. A crude rate of Grade ≥ 3 esophageal toxicity of 6.8% was reported in our institution following single-fraction spine SRS³². Two Grade 4 acute esophageal toxicities, four Grade 4, and one Grade 5 late esophageal toxicities occurred. All of these events occurred in patients with either iatrogenic esophageal manipulation or with a history of radiation recall chemotherapy.

Some evidence suggests that administration of individual radiotherapy doses of 20 Gy or greater per fraction may lead to an increased risk of vertebral compression fracture³³. These findings remain limited as there are few studies that have compared single-fraction and hypofractionated SRS dosing schemes particularly in the post-operative period, thereby underscoring the clinical value of this prospective trial.

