6.2 Subject Exclusion Criteria

- 1) Primary spine tumor
- 2) Age < 18
- 3) Pregnancy
- 4) Lack of adequate (≥ 2 mm) separation between the spinal cord and the tumor on post-operative CT myelogram or MRI perfusion
- 5) Radiosensitizing chemotherapy (taxol, taxotere, cisplatin, gemcitabine, 5-fluorouracil) given within one week of radiation treatment

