The organ at risk tolerances will be different for the two treatment arms and are presented in Appendix G (Single-Fraction) and Appendix H (Hypofractionated). The single-fraction treatment will be administered in one day while the hypofractionated treatment will be administered every other day. Total treatment time per fraction including set up will be 60-75 minutes per fraction.

Nausea, dysphagia and diarrhea will be treated according to standard institutional practice.

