11.0 TOXICITIES/SIDE EFFECTS

11.1 Toxicities/Complications

Subjects will be monitored for surgical complications. Our retrospective study found that major surgical complications occurred in 14.3% patients within 30 days of surgery. Among those patients that suffered complications from surgery within 30 days, Table 2 below depicts the likelihood of complications^{6,39}:

Table 2: Postoperative Complications

wound infection/dehiscence	2.9%
hardware fracture	2.8%
pneumonia	2.1%
pulmonary embolism	2.1%
postop hematoma	0.7%
radiculopathy	0.7%
stroke	0.7%
gastrointestinal bleed	0.7%

Cerebrospinal fluid leak is a rare complication, occurring after less than 5% of operations. Neurologic injury is an exceedingly rare post-operative complication, occurring after far less than 1% of operations.

Patients will also be monitored for radiation toxicity including: acute (\leq 90 days from the start of treatment) and late ($>$ 90 days) toxicity. All patients are going to be monitored for skin, subcutaneous tissue, spinal cord and fracture toxicity. In addition, patients undergoing cervical radiation will be monitored for mucous membrane, pharynx and esophagus, larynx and upper GI toxicity. Patients undergoing thoracic radiation will be monitored for upper and lower GI, lung and heart toxicity. Patients undergoing lumbar radiation will be monitored for genitourinary and lower GI toxicity. The severity of the toxicity will be graded according to Appendix I (Acute Radiation Toxicity) and Appendix J (Late Radiation Toxicity) based on the Radiation Therapy Oncology Group classification schema.

Low-grade radiation-related toxicity may include fatigue, skin erythema, subcutaneous fibrosis and bone pain. More significant toxicity is rare ($<$ 1%) and may include esophagitis,

pericarditis, diarrhea, nausea, vomiting, myelosuppression, myelitis, acute radiation pneumonitis, late pulmonary fibrosis, esophageal stricture, small bowel obstruction and radiation enteritis.

Participants should not be or become pregnant during the course of treatment because the radiation used in this study may be teratogenic. Participating sites should notify the MSK PI if an external participant becomes pregnant.

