patient has multiple eligible lesions, all of them will be treated within the randomized arm and each eligible lesion (non-contiguous lesions treated with a separate radiation contour) will be treated as a separate study unit. After the enrollment of the final patient, a 2-year follow up is planned. Three interim analyses are planned and will be conducted at the time of the DSMB annual review of the study. The O'Brien-Flemming boundary will be applied for assessing statistical significance. Specifically, the rejection regions in terms of the corresponding Z-scores are $Z > 3.09$, $Z > 2.06$, $Z > 1.63$ and $Z > 1.39$ for the three interim looks and the final look, respectively. We expect that very few patients will have multiple lesions and thus we do not plan to examine the correlation among multiple lesions from the same patients. Instead, the analysis of the primary endpoint will be conducted at lesion level as mentioned above. Data will be collected from all four centers and analyzed at MSKCC.

In consideration of the fact that a large cohort will be recruited, this study will be continuously monitored to protect patients from excess toxicity. For each arm, we anticipate that the true rate of any grade 4 toxicity within 24 months post SRS is less than 10%. All grade 4 toxicities or greater observed will be reviewed by the study chair. Moreover, using a stopping rule based on sequential probability ratio test (SPRT), each arm of the study is monitored for any grade 4 or above toxicities that are judged to be associated with the radiation treatment. This stopping rule specifies that for each arm, the study will be halted if any of the following conditions occur: >4 /first 15; >6 /first 35; >9 /first 55; or if more than 12 unacceptable toxicities are observed within 24 months post SRS when the last (75th) patient has completed the trial. When the true toxicity rate is 10%, this stopping rule has a probability of 0.1 to stop the trial. When the true toxicity rate is 20%, this stopping rule has a probability of 0.8 to stop the trial. For this stopping rule we will use each patient as a study unit.

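### Section 11.1 puts significant radiation toxicity, esophagitis included, below 1%, while Section 3.7 reports 6.8% Grade 3 or higher esophageal toxicity after single-fraction SRS

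*Combined protocol and SAP*

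**What the plan says.** Section 11.1 (Toxicities/Complications) first names low-grade effects and then states: "More significant toxicity is rare ($<$ 1%) and may include esophagitis". The same sentence ends with "late pulmonary fibrosis, esophageal stricture, small bowel obstruction and radiation enteritis". It does not define the grade at which toxicity becomes more significant, and it gives one figure for both arms and all spinal levels.

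Section 3.7 (SRS Toxicity Profile) reports: "A crude rate of Grade ≥ 3 esophageal toxicity of 6.8% was reported in our institution following single-fraction spine SRS". It continues: "Two Grade 4 acute esophageal toxicities, four Grade 4, and one Grade 5 late esophageal toxicities occurred", and then: "All of these events occurred in patients with either iatrogenic esophageal manipulation or with a history of radiation recall chemotherapy". For hypofractionated treatment it mentions only single cases of certain Grade 3 events, dysphagia among them, with no denominator.

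Section 14.0 (Biostatistics) adds a third figure: in each arm, the true rate of any Grade 4 toxicity within 24 months is expected to be below 10%.

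Two other places touch on the settings named in Section 3.7. Section 6.2 excludes "Radiosensitizing chemotherapy (taxol, taxotere, cisplatin, gemcitabine, 5-fluorouracil) given within one week of radiation treatment". Section 9.0 says: "Nausea, dysphagia and diarrhea will be treated according to standard institutional practice".

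**The concern.** Section 3.7 is background; Section 11 is the section that sites work from. Section 11.2 defines reportable adverse events as Grade 3 or higher radiation toxicity as set out in Section 11.1. Section 17.2 requires each serious adverse event report to say whether the event was expected, and Section 17.3 makes notice to all sites of treatment-related serious events depend on their being unexpected. Section 17.0 requires potential toxicities to be talked through with the patient at enrollment. In all of these uses, the rate in the safety section is the natural reference.

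If that rate is too low, patients may be told of a smaller risk than the lead institution has itself reported, and sites may differ on whether a Grade 3 or higher esophageal event is expected. Comparing radiation toxicity between the regimens is also the first secondary objective (Section 2.0), so the stated background rate should be clear.

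**Working it through.** **Can either figure be reproduced?** No. The <1% and the 6.8% both stand without numerator or denominator. The check is therefore whether any reasonable reading makes them agree.

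**Inputs.** <1% (Section 11.1); 6.8%, six Grade 4 and one Grade 5 events (Section 3.7); 75 patients per arm (Section 14.0).

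**1. Expected counts in the single-fraction arm** (n × p)
- At 6.8%: 75 × 0.068 = 5.1 patients. P(at least one) = 1 − 0.932^75 = 0.995.
- At 1%, the upper end of Section 11.1: 75 × 0.01 = 0.75 patients. P(at least one) = 1 − 0.99^75 = 0.53.

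**2. Could <1% be an average over the two arms?** Assume no esophageal events at all in the hypofractionated arm: (6.8% + 0%) / 2 = 3.4%. This is still above 1%.

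**3. Could it be an average over spinal levels?** Assume that 6.8% applies only to patients treated near the esophagus and 0% to the rest.
- Single-fraction arm alone: the share treated near the esophagus must be below 1 / 6.8 = 14.7%.
- Both arms together, again with no hypofractionated events: below 1 / 3.4 = 29.4%.

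The protocol gives no such share. Section 11.1 itself sets out monitoring for cervical, thoracic and lumbar fields and does not describe the first two as uncommon.

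**4. Could more significant mean only Grade 4–5?** Section 3.7 counts 2 + 4 + 1 = 7 such events. Assume that they come from the series behind the 6.8% and that each is one patient.
- Seven events cannot exceed the Grade 3 or higher count, so the series has at least 7 / 0.068 ≈ 103 patients.
- For 7 / n to fall below 1%, n must exceed 700, which implies more than 0.068 × 700 = 47.6, so about 48 or more, Grade 3 or higher events.
- Between these limits the Grade 4–5 rate is 6.8% at n = 103, 3.5% at n = 200 and 1.4% at n = 500.

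**5. Could <1% apply to each listed item?** Esophagitis and esophageal stricture together would then stay below 2 × 1% = 2%, still under 6.8%.

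**6. Could it apply only to patients without the two risk settings?** Section 11.1 does not say so. Exclusion 5 in Section 6.2 may overlap with the chemotherapy setting, but it concerns five agents within one week of radiation and not a history of recall chemotherapy. The visible eligibility criteria do not mention esophageal manipulation.

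**The case against.** The strongest reply is that the two figures need not describe the same patients. The 6.8% is a crude rate with no stated denominator, dose or spinal level, and the title of its source in the reference list concerns paraspinal radiosurgery. The trial also treats lumbar fields, and Section 3.7 ties events to particular settings. This stands as far as size is concerned: a reader might infer a fixed seven-fold understatement, but the ratio holds only if the populations match, which the documents do not show. It does not remove the conflict, because Section 11.1 states no limit of population.

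It is also fair to say that sites hold the whole protocol, Section 3.7 included. Other safeguards act on grade whatever rate is printed: Grade 3 or higher radiation toxicity is reportable within 14 days (Section 11.2), the study chair reviews every Grade 4 or higher event (Section 14.0), and Grade 4–5 toxicity resulting from treatment is handled as serious (Section 17.2). These protect patients after an event. They do not correct the risk stated beforehand.

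Four stronger readings are tempting but lack support:
- **That the arms differ in esophageal risk.** No hypofractionated esophageal rate is given; single cases without a denominator do not show a lower one.
- **That the stopping rule leaves a gap.** An exact calculation of the rule gives 0.088 at a true rate of 10% and 0.822 at 20%, in line with the stated 0.1 and 0.8. It gives 0.012 at 6.8%, but that enters a Grade 3 or higher rate into a rule for Grade 4 or higher events. Rarely halting below 10% is what the rule is meant to do.
- **That treating dysphagia by institutional practice leads patients into the risk setting.** Nothing in Section 9.0 says that this practice involves esophageal manipulation.
- **That patients are not warned.** The consent text and the contents of Appendices E and G to J are not in the text available for review, so their silence cannot be claimed.

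**Conclusion.** The conflict is real, and Section 11.1 is wrong as written. An unqualified <1% for a list that includes esophagitis and stricture cannot stand beside the lead institution's own 6.8% for one organ after one of the randomized regimens. Among 75 single-fraction patients the difference is about 5 affected against fewer than 1. That count assumes that the 6.8% carries over to this trial; the true number depends on spinal levels and risk settings that the documents do not give. Averaging over arms does not bring the rate below 1%, and averaging over levels does so only if fewer than 14.7% of single-fraction patients are treated near the esophagus.

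It is also unclear whether the statement in Section 3.7 about esophageal manipulation and recall chemotherapy covers every Grade 3 or higher event or only the seven of Grade 4–5. The point concerns the stated safety risk only; sample size, power and the primary analysis do not depend on it.

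**What to change.** 1. In Section 11.1, replace the unqualified <1% with figures consistent with Section 3.7. State grade, regimen, spinal level and source population for each, and reconcile them with the Grade 4 expectation in Section 14.0. If no hypofractionated esophageal rate is available, say so.
2. Use the same figures in the enrollment discussion under Section 17.0 and when judging expectedness under Sections 17.2 and 17.3.
3. Repeat in Section 11.1 the statement from Section 3.7 on the two settings in which events occurred, and make clear which grades it covers.
4. Reconcile Section 3.7 with Exclusion 5 in Section 6.2 and with the symptom-treatment sentence in Section 9.0. Whether any clinical rule follows is for the investigators to decide.

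The cost is amended safety text and a less favorable stated risk.

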11.2 Adverse Events (AE)

Defined

An adverse event is defined as the appearance of (or worsening of any pre-existing) undesirable sign(s), symptom(s), or medical condition(s) that occur after treatment. For this study, we consider reportable adverse events to include radiation Grade 3 (and above) toxicity as enumerated in Section 11.1. Adverse events should be reported to both the site PI and the MSK PI, please see Section 16.0.3.

Reporting Requirements

For non-serious adverse events, we will only be capturing toxicities that are possibly related to study participation. Adverse event monitoring will be continued for 24 months following the completion of SRS treatment or until the time of death if death occurs prior to the 24 month follow-up. Adverse events should be described using a diagnosis whenever possible, rather than individual underlying signs and symptoms. When a clear diagnosis cannot be identified, each sign or symptom should be reported as a separate Adverse Event. Adverse events will be reported within 14 days.

Adverse events will be assessed by the investigators according to the National Cancer Institute Common Terminology Criteria for Adverse Events (CTCAE) version 4.0 (<http://ctep.info.nih.gov>). If CTCAE grading does not exist for an adverse event, the severity of mild, moderate, severe, and life-threatening, corresponding to Grades 1-4, will be used.

As far as possible, each adverse event should be evaluated to determine:

1. The severity grade (CTCAE Grade 1-4)
2. Its duration (start and end dates or Ongoing at End of Study)
3. Its relationship to the study treatment (reasonable possibility that AE is related to study: No, Yes)
4. Action taken with respect to study (none, dose adjusted, temporarily interrupted, permanently discontinued, unknown, not applicable)
5. Whether medication or therapy was given (no concomitant medication/non-drug therapy, concomitant medication/non-drug therapy)
6. Whether it is serious, where a SAE is defined as in Section 17.2 (SAE)

All adverse events should be treated appropriately. If a concomitant medication or non-drug therapy is given, this action should be recorded on the Adverse Event form in CRDB. Once an adverse event is detected, it should be followed until its resolution or until it is judged to be permanent.

12.0 CRITERIA FOR THERAPEUTIC RESPONSE/OUTCOME ASSESSMENT

The primary study endpoint, which is local tumor control, will be radiographically determined according to routine standard of care post-surgical and post-treatment imaging (MRI or CT) of the spine. Local tumor control will be defined as the lack of local tumor progression at the irradiated site on follow-up imaging. All imaging studies from collaborating institutions will be submitted for central review at MSK. T1, T1 gadolinium enhanced, T2 and STIR MR sequences will be used for follow-up imaging in order to monitor treatment response. 3-5mm slice thickness on MR imaging will be used. We will avoid strict imaging parameter restrictions since several medical centers will take part in the study and it will be challenging to strictly confine imaging criteria. Standard MRI sequences will be sufficient in order to monitor for recurrence. Volumetric measurements will not be used in this protocol. CT will be used in patients who cannot undergo MR imaging.

Each month, the imaging studies from participating sites will be batched and submitted through MSK's FTP Imaging Secure File Transfer system to the MSK PI. These scans should be de-identified prior to submission to MSK. The study RSA will transfer images to MSK's electronic Research PACS system. Central review will be carried out at two week intervals by MSK neuroradiologists ([name] and [name]) with expertise in interpretation of spinal oncology imaging. In cases of disagreement of the initial radiology read and central review interpretation, the results will be discussed with the treating surgeon or radiation oncologist in order to reach agreement. Site investigators will be notified of the review results within 24 hours. The turn-around time for central imaging review will be 14 days. Progression will be defined quantitatively as a 15% increase in maximal horizontal and vertical diameter, when not accounted for by fracture or evolving treatment change. The duration of response will be measured as lack of progression on imaging or until the last follow-up visit.

Secondary endpoints will include clinical determination of MRC muscle strength assessment, ECOG, ASIA, and treatment-related toxicity at each follow-up visit.

Secondary endpoint comparison of quality of life between the two cohorts will be determined through optional patient-reported responses for the MDASI - Spine Tumor Module at each follow up visit. The MDASI Spine Tumor Specific Items (questions #14-18) will be scored separately as a Spine Tumor Symptom Severity scale.

Secondary endpoint comparison of pain control will be determined through optional patient-reported responses of the BPI. Pain severity at its worst (question #5) and the average of the pain interference (average of question #9) will serve as the pain endpoints.

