1.0 PROTOCOL SUMMARY AND/OR SCHEMA

Metastatic disease of the spine affects nearly 20% of patients with cancer and poses a growing problem as improved neo-adjuvant strategies allow longer life expectancy.

This is a Phase III multicenter clinical trial designed to prospectively evaluate the comparative effectiveness of single-fraction and hypofractionated stereotactic radiosurgery (SRS) in patients who underwent decompressive surgery for spinal metastases with a primary endpoint of local tumor control. Secondary objectives will evaluate complications and quality of life measures. Collaborating institutions include Massachusetts General Hospital (MGH), Johns Hopkins University (JHU), and Stanford University.

Eligible patients will have undergone spinal decompressive surgery for the treatment of high grade metastatic epidural spinal cord compression and demonstrate post-operative separation between tumor and the spinal cord on CT myelogram or MRI perfusion. This is a non-inferiority study in which patients will be randomized in a 1:1 ratio to undergo either single-fraction SRS (24 Gy) or high-dose hypofractionated SRS (27 Gy in 3 fractions) within 8 weeks of surgery. The treatment duration will be 1 to 7 days.

Study enrollment of 150 patients will be completed within two years. After randomization, patients will be followed up at 3, 6, 9, 12, 18, and 24 months (± 8 weeks) when possible or until death. The study duration will be up to four years. The primary endpoint will be local tumor control after SRS as monitored through imaging at follow up.

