10.0 EVALUATION DURING TREATMENT/INTERVENTION

Pre-treatment evaluations may be performed within 8 weeks of consent. After SRS, patients will be closely monitored for any evidence of toxicity, systemic illness or tumor progression. Acute toxicity assessment (see Appendix E) will occur by phone or clinic visit within 4 weeks (± 10 days) after the completion of radiotherapy. Follow-up clinic visits will take place 3 months, 6 months, 9 months, 12 months, 18 months and 24 months (± 8 weeks) after the completion of radiotherapy. At each follow-up visit, the investigators will complete the Spine Clinic Assessment form (see Appendix F). Spine MRI or CT will also be performed at the time of each follow-up, in accordance with routine standard of care.

Table 1: Pre-therapy and Follow-up Evaluations

Item	Pre-therapy (w within 8 weeks of consent)	Follow-up (3, 6, 9, 12, 18, 24 months \pm 8 weeks after the completion of SRS)
Inclusion/exclusion criteria	X	
CT myelogram or MRI perfusion	X	
Pathology diagnosis confirming metastatic disease	X	
Medical history	X	
Pregnancy test ¹	X	
Physical exam	X	X
Concomitant medications review	X	X
ECOG	X	X
Quality of Life assessments (MDASI and BPI) ²	X	X
Spine Clinic Assessment Form	X	X
MRI/CT scan ³	X	X
Adverse-event/toxicity assessment ⁴	X	X
Consent	X	

¹ For women of child-bearing potential, a urine or blood pregnancy test must be completed within 2 weeks prior to SRS.

- ² Patients will be asked to complete quality of life (MDASI and BPI) assessments at all timepoints, however this will remain optional. In instances where these questionnaires are not available in the participant's primary language, the participant will not be required to complete the questionnaire(s).
- ³ All patients are required to have MRI/CT based imaging at baseline and 3, 6, 9, 12, 18, and 24 months (\pm 8 weeks) after SRS. The imaging modality should remain constant for each patient throughout.
- ⁴ Only treatment-related adverse events will be reported. Acute toxicity assessment (see Appendix E) will occur by phone or clinic visit within 4 weeks (\pm 10 days) after the completion of radiotherapy.

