An intent-to-treat, stratified log rank test will be used to test whether or not the single-fraction SRS arm is inferior to the hypofractionated (3 fractions in total) SRS arm in terms of the local control rate. To set up a formal test we will use the 1-year local control rate as the surrogate of the efficacy (assuming that the two survival curves follow exponential distributions) and allow a 10% inferior margin. From a clinical standpoint, the investigators agreed that a difference of less than 10% is not regarded as significant. On this basis, we permit a 10% inferior margin. I.e., we will test $H_0: P_1 \leq (P_2 - 10\%)$ vs $H_1: P_1 > (P_2 - 10\%)$, where P_1 and P_2 denote the 1-year local control rate for the single-fraction arm and the 3-fraction arm, respectively. To approximately assess the power of the test, we estimate that the 3-fraction arm will yield a 1-year local control rate around 85% based on interim preliminary data from a multicenter Phase III trial (Protocol 10-154), and set the type I error (that is, declare single-fraction arm noninferior while it is not) rate at 0.10. When the two arms have equal efficacy, i.e., $P_1 = P_2 = 85\%$, the power (that is, declare the single-fraction arm noninferior while it is) of this noninferiority test⁴⁰ is 80% when there are 75 patients in each arm. Besides, since deaths without local failure are likely, competing risk analysis will also be used to estimate the local control rates of the two arms over time. We plan to enroll 150 patients within 2 years. If a

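### Control time for lesions without progression ends at the last visit, not the last evaluable scan, so local control can be overstated when a visit lacks a readable scan

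*Combined protocol and SAP*

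**What the plan says.** Section 12.0 makes the primary endpoint an imaging finding: "Local tumor control will be defined as the lack of local tumor progression at the irradiated site on follow-up imaging". After defining progression, the same section says when a patient's time ends: "The duration of response will be measured as lack of progression on imaging or until the last follow-up visit".

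Visits and scans are meant to coincide. Section 10.0 says "Spine MRI or CT will also be performed at the time of each follow-up, in accordance with routine standard of care", and footnote 3 to Table 1 says "All patients are required to have MRI/CT based imaging at baseline and 3, 6, 9, 12, 18, and 24 months", within a window of 8 weeks either side. Section 1.0 qualifies the follow-up schedule with "when possible or until death".

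Section 14.0 uses a stratified log-rank test to "test whether or not the single-fraction SRS arm is inferior to the hypofractionated (3 fractions in total) SRS arm". The hypotheses are written on the 1-year local control rate and "allow a 10% inferior margin". It adds a competing-risk estimate because deaths without local failure are expected. It gives neither an event date nor a censoring date. No section says what happens when a scan is missed or cannot be read.

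**The concern.** A visit without a readable scan says nothing about the endpoint. If time still runs to that visit, the lesion stays in the risk set as failure-free over a period when nobody looked, and the estimated failure rate falls.

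The documents give reasons to expect some missed scans. Entry allows ECOG up to 3 and a life expectancy from 3 months (Section 6.1). Quoted median survival is 7.0-16.5 months (Section 3.1). Inability or loss to follow-up is a listed reason for removal (Section 13.0). Table 6 asks for an outcome form at off study but appears to ask for no imaging there.

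The reported 1-year and 2-year control rates are at stake in both arms. If scans are missed more in one arm, the comparison is affected too, because the arm with more missed scans looks better controlled. That is possible here: Sections 3.7, 3.9 and 14.0 all raise a higher fracture risk with single-fraction treatment, and Section 12.0 makes fracture a complication in reading progression.

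**Working it through.** **The plan's own figure.** With exponential control times, the margin as a hazard ratio is ln(0.75)/ln(0.85) = 1.770. The failure hazard is -ln(0.85) = 0.1625 per year. With uniform accrual over 2 years, 2 further years of follow-up and no deaths or dropout, the event probability is 1 - (exp(-2 x 0.1625) - exp(-4 x 0.1625))/(2 x 0.1625) = 0.383, so 150 patients yield 57.5 events. Section 14.0 states: "set the type I error (that is, declare single-fraction arm noninferior while it is not) rate at 0.10". At one-sided 0.10:

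- Schoenfeld form: sqrt(57.5/4) x ln(1.770) - 1.282 = 0.88, power 81.1%.
- Freedman form: sqrt(57.5) x 0.770/2.770 - 1.282 = 0.83, power 79.6%.

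Both agree with the stated 80%. No visit or scan attendance enters this calculation, so the censoring rule does not change the planned sample size or stated power. Ignoring deaths in the power calculation is a separate matter.

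**Comparing the two rules.** Simulation of 400,000 patients per scenario:

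- From the documents: 85% 1-year control with exponential times; visits at 3, 6, 9, 12, 18 and 24 months; median survival 7.0 or 16.5 months.
- Assumed: exponential survival; visits attended while alive; 10-30% of scans missed at random at attended visits.
- Progression is dated to the first scan done after it occurs. Event-free patients are censored at the last attended visit or at the last scan done. Deaths end follow-up by censoring.

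Kaplan-Meier local control (%), with the excess in percentage points:

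| Median survival (months) | Scans missed | 12 mo, visit | 12 mo, scan | Excess | 24 mo, visit | 24 mo, scan | Excess |
|---|---|---|---|---|---|---|---|
| 16.5 | 0% | 85.00 | 85.00 | 0 | 72.25 | 72.25 | 0 |
| 16.5 | 10% | 85.44 | 85.22 | 0.2 | 72.99 | 71.96 | 1.0 |
| 16.5 | 20% | 86.00 | 85.49 | 0.5 | 74.02 | 71.65 | 2.4 |
| 16.5 | 30% | 86.42 | 85.49 | 0.9 | 74.74 | 70.61 | 4.1 |
| 7.0 | 0% | 85.05 | 85.05 | 0 | 72.24 | 72.24 | 0 |
| 7.0 | 10% | 85.37 | 84.90 | 0.5 | 72.75 | 71.36 | 1.4 |
| 7.0 | 20% | 85.79 | 84.73 | 1.1 | 73.86 | 70.77 | 3.1 |
| 7.0 | 30% | 86.48 | 84.69 | 1.8 | 74.55 | 69.30 | 5.3 |

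With no deaths, the 12-month excess is at most 0.13 points.

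**Reading the table.** The excess is visit rule minus scan rule, not visit rule minus truth. At 16.5 months and 30% missed, the visit rule is 74.74 - 72.25 = 2.5 points above the complete-imaging value at 24 months, and the scan rule is 72.25 - 70.61 = 1.6 points below it. The scan rule is not exact, because a progression missed at one scan is dated to a later one.

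**Sustained missingness.** If 10-30% of patients stop imaging after month 3 but keep attending (16.5-month survival), the excess at 12 months runs from 86.13 - 85.04 = 1.1 to 88.40 - 85.12 = 3.3 points. At 24 months it runs from 74.82 - 72.48 = 2.3 to 79.61 - 72.55 = 7.1 points. Here the scan rule stays close to the complete-imaging values.

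**Unequal missingness.** With truly equal arms, 30% missed in one and 10% in the other (16.5-month survival), the spurious 12-month difference is about 1.2 points under the visit rule and 0.5 under the scan rule. Changing the rule removes about 0.7 points, against a 10-point margin.

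**The case against.** **Scans are required at every visit.** Section 10.0 and footnote 3 to Table 1 do require this. Where it is followed, the last visit and the last scan coincide and nothing is overstated. This stands, and it makes the concern conditional. It does not remove it, because a censoring rule exists for the cases where the schedule fails.

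**The sentence concerns duration of response, and Section 14.0 does not cite it.** This also stands: applying it to the log-rank test is an inference. But it is the only rule in the plan for when a patient's time ends. If it does not govern the primary analysis, that analysis has no censoring rule and needs the same edit.

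**Deaths are handled as competing events.** In that analysis a patient who dies without recorded progression has an event at death, so the choice of date matters mainly for patients still alive. Patients too ill to be scanned may also miss the visit, and then no unscanned visit time is credited. This narrows the problem, but the log-rank test still needs a date.

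**A larger bias might be inferred.** A reader might spread credited time over a constant hazard. With 7-month median survival, mean time at risk to failure, death or 2 years is 0.69 years. If 30% of patients are each credited 6 months, the hazard shrinks by (0.69 - 0.30 x 0.5)/0.69 = 0.78. Then 85% becomes 88.1%, 75% becomes 79.8%, and a true 10-point deficit reads as 8.2. The documents do not support this, for three reasons:

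- On the nominal schedule, one missed scan leaves a 6-month gap only after month 12, which cannot move a 12-month Kaplan-Meier estimate. Section 14.0 uses the exponential assumption to set up the test and its power and does not name it as the estimator.
- At a 7-month median only 0.5^(18/7), about 17%, reach month 18, so 30% cannot have such a gap from one missed scan.
- Multiplying both hazards by one factor leaves their ratio at 1.77, and the planned test is a log-rank test.

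**Conclusion.** The concern holds as a conditional one. Section 12.0 ends the control time of a non-progressor at a date that may carry no information on the endpoint, and Section 14.0 supplies no alternative. Local control can therefore be overstated when attended visits lack an evaluable scan.

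The size rests on the assumed 10-30% of scans missed at random and on exponential survival with a median of 7.0-16.5 months. On those assumptions the visit rule exceeds the scan rule by about 0.2-1.8 points at 12 months and 1.0-5.3 points at 24 months. Larger gaps need patients who stop imaging early yet keep attending.

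A reader might infer that the control rates are overstated as a matter of fact, or that the non-inferiority decision is materially biased. The documents support neither. They require a scan at each visit, and equal missingness largely cancels in the log-rank comparison. The unequal-missingness case tested moves the 12-month difference by little against the margin. The change is still worth making because the rule is wrong for an imaging endpoint and is easily corrected.

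**What to change.** Replace the sentence in Section 12.0, and put the matching rule in Section 14.0, along these lines: time to local progression runs to the date of the first scan showing progression on central review, and lesions without progression are censored at the date of the last evaluable scan of the treated level.

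In the competing-risk analysis, keep death without recorded progression as the competing event. Report by arm how many such deaths had no evaluable scan within one scheduled interval before death. Because the scan rule can itself read slightly low at 24 months, an interval-censored estimate would be a reasonable optional sensitivity analysis.

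The cost is one sentence in each section and one descriptive count. Imaging is already submitted to the coordinating center under Section 12.0 and Table 6, and neither the sample size nor the stated power changes. The downside is slightly shorter follow-up time and slightly lower reported control.
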